### **8.3.12 Assessments**

#### **8.3.12.1 Medical history**

Relevant medical history/current medical condition data includes data regarding ongoing or significant previous ophthalmic and general medical conditions and procedures until start of ARGOS-SC pressure sensor implantation. Relevant medical history should be supplemented by review of the subject's medical chart and/or by documented dialog with the subject's referring physician. If possible, diagnoses and not symptoms are to be recorded.

#### **8.3.12.2 Concomitant medication, treatments and devices**

There are no restrictions for the use of concomitant medications required for ophthalmologic or systemic diseases during this clinical investigation. All medications including non-prescription medications used by the subject during the trial and medications in use at enrollment, will be documented in the subject's file and in the CRF, as will all diagnostic procedures and medical interventions.

#### **8.3.12.3 AEs/ADEs/SAEs/SADEs**

All AEs/ADEs/SAEs/SADEs will be recorded.

 IOP Implantdata Ophthalmic Products GmbH	Clinical Investigation Plan ARGOS-SC01_Follow-up	Revision C  Page 60 of 97
--	---	---------------------------------

#### **8.3.12.4 Device Deficiencies**

A device deficiency form will be completed and sent to the sponsor for all observed device malfunctions or deficiencies, including defects in devices that have not been implanted in a subject or used otherwise. Starting with the implantation of the ARGOS-SC implant, all relevant malfunctions will also be recorded in the subject's chart and CRF. Reasonable deviations from GAT measurements or reasonable intraserial ARGOS-SC measurement variability is not classified as a Device Deficiency.

#### **8.3.12.5 Acceptance Questionnaires ARGOS-SC**

In the study, two types of questionnaires will be used to assess potential strengths and weaknesses of the ARGOS-SC system. At V13 (Month 36), the investigator responsible for IOP measurement as well as the patients will be asked to complete a user acceptance questionnaire for the MESOGRAPH reading device and the general measurement procedure.

The aim of these questionnaires is to gain more information about the level of user-acceptance of the ARGOS-SC system during implantation and during IOP measurement. The data collected with these questionnaires is only of exploratory nature and will not be included in the analysis. Results will provide the sponsor with data that could influence future device system improvements.

#### **8.3.12.6 National Eye Institute – Vision related Quality of Life Questionnaire-25 (VFQ-25)**

The VFQ-25 is a standardized questionnaire about quality of life relating to the patient's vision. It should be completed by the patient at V11 and V13.

#### **8.3.12.7 Visual Acuity (VA)**

The best corrected visual acuity will be determined after objective and subjective determination of refraction with the ETDRS chart in accordance with the ETDRS protocol of **both eyes**. The number of character read and the reading distance will be recorded. The standard testing distance is 4 meters.

#### **8.3.12.8 Visual Field (Perimetry)**

The purpose of visual field testing is to determine both the outer limits of visual perception by the peripheral retina and the varying qualities of vision within that area. Perimetry is performed to obtain an accurate examination of the peripheral extent of the visual field. Automated perimeters will be used either with standard glaucoma field, field 30-2 or equivalent. This should always be done on **both eyes** in order to compare study and fellow eye.

 Implantdata Ophthalmic Products GmbH	Clinical Investigation Plan ARGOS-SC01_Follow-up	Revision C  Page 61 of 97
---	---	---------------------------------

A change of the perimeter during the study should be avoided.

#### **8.3.12.9 External Eye Photography**

External eye photography will be performed through a slit lamp camera or equivalent in order to document potential changes to the outer eye.

#### **8.3.12.10 Heidelberg Engineering ANTERION® (if available)**

The ANTERION® from Heidelberg Engineering will be used for determination of the ARGOS-SC location (only at sites where it is available).

#### **8.3.12.11 Anterior eye segment measurement of both eyes**

##### **Slit-lamp biomicroscopy (undilated, anterior segment)**

At every visit, the external ocular structures and the front of the eye will be assessed using the slit-lamp biomicroscopy according to standard site procedures. Particular attention will be paid to the ocular surface and possible effects of the ARGOS-SC. The following structures will be assessed:

- a) Lids
- b) Conjunctiva (*irritation*)
- c) Cornea
- d) Anterior chamber (*cells/flares (SUN-Classification), fibrin, flattening*)
- e) Iris
- f) Pupil
- g) Lens
- h) Anterior vitreous body (*cells/haze (NIH-Grading)*)

##### **Optical Coherence Tomography (OCT)**

Anterior Segment OCT will be used to evaluate effects on change in chamber angle and after non-penetrating glaucoma surgery and to assess the central corneal thickness.

##### **Gonioscopy**

Standard gonioscopy will be used to confirm glaucoma classification and to assess other problems within the anterior chamber, such as the presence of foreign bodies hidden in the recess of the angle. The gonioscopic grading system according to Shaffer is used in this study.

 Implantata Ophthalmic Products GmbH	Clinical Investigation Plan ARGOS-SC01_Follow-up	Revision C  Page 62 of 97
--	---	---------------------------------

### 8.3.12.12 Posterior eye segment measurement of both eye

#### Biomicroscopy (dilated, fundus)

The posterior eye segment will be examined using a slit lamp in combination with a 90D or “Superfield” or comparable lenses. The following parameters will be assessed:

- a) Optic nerve lesions
- b) Other posterior pole lesions
- c) Vitreous opacities
- d) Optic nerve head
- e) Fundus lesions
- f) Retinal arteries and veins (AV)
- g) Macular area
- h) Fundus periphery
- i) Normal and abnormal variations of the fundus.

#### Optical coherence tomography (OCT)

Posterior segment OCT will be used to assess both macular structures and the peripapillary nerve fiber layer (RNFL).

If available, the Heidelberg Engineering Spectralis Glaucoma-Module Premium Edition (Minimum rim width at Bruch membrane opening (BMO-MRW), RNFLT and macula)) should be used. This should always be done on **both eyes** in order to compare study and fellow eye.

#### Fundus photography

Standard fundus photography will be performed at V11 and V13 to document potential changes to the interior surface of the eye, including the retina. Additionally, a photo of the optic nerve and nerve fiber layer will be performed in red-free illumination.

### 8.3.12.13 Intraocular pressure (IOP) measurement of both eyes

Intraocular pressure will be measured using three techniques. GAT will be performed in the clinic at every visit and if available, DCT. ARGOS-SC measurements will be performed in the clinic at every visit and by the patient at home between the visits. Only GAT will be used to guide any treatment decisions. The GAT and DCT must be performed by as few dedicated investigators as possible at each site to reduce potential bias.

 Implantdata Ophthalmic Products GmbH	Clinical Investigation Plan ARGOS-SC01_Follow-up	Revision C  Page 63 of 97
---	---	---------------------------------

### **IOP measurement in the clinic**

IOP measurement will be conducted as a series of 2x GAT (in case of a difference of more than 2mmHg, a third GAT-measurement is required) followed by 3x ARGOS-SC system. When series of measurements are made, GAT must always be used first to avoid potential operator bias. For the ARGOS-SC measurements the patient has to stay in the same position as for the GAT-measurements (chin on chin rest, forehead installed).

Additionally (if available), a series of 2x DCT (in case of a difference of more than 2mmHg, a third DCT-measurement is required) followed by 3x ARGOS-SC will be performed after the series of GAT and ARGOS-SC measurements. For the ARGOS-SC measurements, the patient has to stay in the same position as for the DCT-measurements (chin on chin rest, forehead installed).

### **ARGOS-SC system measurement by the subject at home**

Subjects will receive detailed instruction in the use of the MESOGRAPH reading device. Subjects will be requested to perform at least 4 IOP measurements daily with the MESOGRAPH, one each in the morning after getting up, at noon, in the afternoon and in the evening before going to bed.

No data will be recorded manually by the subject. The MESOGRAPH reading device, which is capable of storing up to 3,000 measurements, will be connected to an external GSM module, which will transfer the measured value directly to a secure database. Investigators can log into the database in order to track the pressure levels of their patients as required.

The MESOGRAPH will also be brought to every visit, at which time site staff will assess its functionality and delete recorded IOP data from its memory.

#### **8.3.13 Surgery**

No additional surgery is necessary in the ARGOS-SC01\_Follow-up study, as the included patients have already received an implantation of the ARGOS-SC sensor in the ARGOS-SC01 study.

IOP Implandata Ophthalmic Products GmbH	Clinical Investigation Plan ARGOS-SC01_Follow-up	Revision C
		Page 64 of 97

### **8.3.13.1 ARGOS-SC pressure sensor explantation, if medically necessitated**

---

**Note:** It is not necessary to explant an ARGOS-SC implant which is either non-functional or is known to function incorrectly. The malfunctioning device may safely remain in the eye.

---

Explantation of the ARGOS SC sensor can be performed if the implant poses a medical risk and the treating ophthalmologist deems it necessary. The explantation should only take place if the benefits outweigh the risks. The investigator is responsible for notifying the sponsor of such a procedure immediately upon gaining knowledge of it.

In the event that the sensor has to be explanted, a scleral incision of 4.5 to 5 mm is made above the pars plana at the short side of the sensor, preferably above it. The incision must be fully opened to ensure a safe explantation procedure. A hyaluronic acid-based viscoelastic (see implantation) is then inserted in the suprachoroidal space to ensure complete separation of the sclera and the choroid.

Following explantation, the scleral incision should be sealed using at least one suture.

The explanted device will be returned to Implantata Ophthalmic Products GmbH for analysis.

For the detailed ARGOS-SC explantation, please see "*IFU ARGOS-SC Implant*).

 Implantata Ophthalmic Products GmbH	Clinical Investigation Plan ARGOS-SC01_Follow-up	Revision C
		Page 65 of 97

### 8.3.14 Study Visits

Assessments and procedures to be performed at each visit are indicated with an X in the assessment schedule in Table 4 (see also Section 8.3.12 Assessments). The visits should be arranged as closely as possible to the specified visit day, accepted tolerances are set up for every visit (see Table 4).

**Table 4: Assessment Schedule ARGOS-SC01\_Follow-up**

Visit	V09	V10	V11	V12	V13
Indicative Days (D) Visit window	Last Visit of ARGOS- SC01 (Baseline)	Month 18 (Day 540) +/- 3 weeks	Month 24 (Day 720) +/- 3 weeks	Month 30 (Day 900) +/- 3 weeks	Month 36 (Day 1080) +/- 3 weeks
General					
Informed consent signed	X				
Inclusion & exclusion criteria	X				
Past and current significant medical history	X				
Vision related Quality of Life (VQoL) questionnaire	X		X		X
Visual acuity (ETDRS)  (OU)	X	X	X	X	X
Perimetry  (OU)	X	X	X	X	X
Heidelberg Engineering ANTERION®	X	X	X	X	X
External eye photography 	X	X	X	X	X
User acceptance questionnaire (patient)	X				X
User acceptance questionnaire (investigator)	X				X
Concomitant medication	X	X	X	X	X
AE/ADE/SAE/SADE	X	X	X	X	X
Device malfunction	X	X	X	X	X
Anterior Segment (OU)					
Optical Coherence Tomography 	X	X	X	X	X
Slit-lamp biomicroscopy 	X	X	X	X	X
Gonioscopy 	X	X	X	X	X
Posterior Segment (OU)					
Funduscopy 	X	X	X	X	X
Optical coherence tomography (OCT) 	X	X	X	X	X
Fundus photography 	X		X		X

 Implantdata Ophthalmic Products GmbH	Clinical Investigation Plan ARGOS-SC01_Follow-up	Revision C  Page 66 of 97
---	---	---------------------------------

Visit	V09	V10	V11	V12	V13
Indicative Days (D) Visit window	Last Visit of ARGOS- SC01 (Baseline)	Month 18 (Day 540) +/- 3 weeks	Month 24 (Day 720) +/- 3 weeks	Month 30 (Day 900) +/- 3 weeks	Month 36 (Day 1080) +/- 3 weeks
IOP Measurements					
Goldmann Applanation Tonometry  (OU)	X	X	X	X	X
Pascal Dynamic Contour Tonometry  (OU)	X	X	X	X	X
ARGOS-SC pressure sensor measurement 	X	X	X	X	X
ARGOS-SC pressure sensor self- measurement 	X	X	X	X	X

 The best corrected visual acuity will be determined after objective and subjective determination of refraction with the ETDRS chart in accordance with the ETDRS protocol.

 Perimetry is performed to obtain an accurate examination of the peripheral extent of the visual field. Automated perimeters will be used either with standard glaucoma field, field 30-2 or equivalent.

 External eye photography is performed through a slit lamp camera or equivalent. The outer eye shall be photographed in order to document potential changes to the iris or pupil structure.

 Anterior segment OCT is performed to evaluate effects on change in chamber angle after non-penetrating glaucoma surgery and to assess corneal thickness.

 Slit-lamp biomicroscopy is performed through an undilated pupil to assess the following anatomic parameters of the anterior segment: lids, conjunctiva, cornea, anterior chamber, iris, pupil, lens and anterior vitreous body.

 Standard gonioscopy is used to confirm glaucoma classification and to evaluate the presence of iris tumors, foreign bodies, anterior synchiae and to predict the anterior chamber angle. The gonioscopic grading system according to Shaffer is used in this clinical investigation.

 Funduscopy is performed by means of indirect ophthalmoscopy on a slit lamp with the aid of a 90D or "Superfield" or comparable lenses. For this examination the pupil needs to be dilated by the use of mydriatic agents. This method is used to evaluate the following parameters: optic nerve lesions, other posterior pole lesions, vitreous opacities, optic nerve head, fundus lesions, retinal arteries and veins (AV), macular area, fundus periphery, normal and abnormal variations of the fundus.

 Posterior segment OCT is used to assess macular structures and the peripapillary nerve fiber layer thickness (RNFLT) and if possible Minimum rim width at Bruch membrane opening (BMO-MRW).

 The fundus should be photographed in order to document potential changes to the optic nerve (cup/disc ratio) and nerve fiber layer (red-free illumination).

 IOP measurements will be made in series of 2 GAT measurements (in case of a difference of more than 2 mmHg, a third GAT measurement is required) followed by 3 directly consecutive ARGOS-SC system measurements; *if DCT is available*: additionally followed by 2 Pascal DCT measurements (in case of a difference of more than 2 mmHg, a third Pascal DCT measurement is required) and 3 directly consecutive ARGOS-SC system measurements.

For the non-study eye, only GAT and DCT measurements will be performed as described above.

All measurements should be performed directly one after another.

 All patients will receive a MESOGRAPH reading device after implantation in order to measure the IOP daily at home. Measurements will be taken at least 4 times per day (morning, noon, afternoon, evening). The MESOGRAPH reading device will be connected to an external GSM module, which will transfer the measured value directly to a secure database. Investigators can log into the database in order to track the pressure levels of their patients as required.

 Implantata Ophthalmic Products GmbH	Clinical Investigation Plan ARGOS-SC01_Follow-up	Revision C  Page 67 of 97
--	---	---------------------------------

### 8.3.15 Visit 09 (Month 12/Day 365)

V09 of ARGOS-SC01 is the baseline visit of ARGOS-SC01\_Follow-up. At the Baseline visit, the investigator will conduct the informed consent process (section 11.1), ensuring that the subject's signature has been obtained on the patient informed consent (PIC) form and that the subject has received a copy before any study specific procedures are conducted. Once the PIC is signed, the subject will keep his assigned patient number from the ARGOS-SC01 study assigned (section 8.3.8).

In addition, the following procedures will be performed at this visit:

- Past and current significant medical history
- Recording of AEs/SAEs/ADEs/SADEs, concomitant medications and device malfunctions
- VQoL questionnaire
- User acceptance questionnaire (Investigator)
- User acceptance questionnaire (patient)
- Visual acuity (ETDRS) (OU)
- External eye photography
- Heidelberg Engineering ANTERION® (if available)
- Perimetry (OU)
- Anterior Segment assessments: slit-lamp biomicroscopy, AS-OCT), gonioscopy (OU)
- Posterior Segment assessments: funduscopy, PS-OCT, fundus photography (OU)
- IOP Measurement: GAT (OU) and ARGOS-SC. If available: Pascal DCT (OU)
- Patient ARGOS-SC self-measurements
- Remind subjects to promptly report any SAE that may occur at any time during the study.
- Complete the CRF and arrange the next visit.

### 8.3.16 Semiannual Follow-up visits V10 – V13 (Month 18 – Month 36)

Procedures to be conducted at the visits include:

- Recording of AEs/SAEs/ADEs/SADEs, concomitant medications and device malfunctions
- VQoL questionnaire (V11, V13)
- User acceptance questionnaire (Investigator) (V13)

 Implantdata Ophthalmic Products GmbH	Clinical Investigation Plan ARGOS-SC01_Follow-up	Revision C  Page 68 of 97
---	---	---------------------------------

- User acceptance questionnaire (patient) (V13)
- Visual acuity (ETDRS) (OU)
- External eye photography
- Heidelberg Engineering ANTERION® (if available)
- Perimetry (OU)
- Anterior Segment assessments: slit-lamp biomicroscopy, AS-OCT), gonioscopy (OU)
- Posterior Segment assessments: funduscopy, PS-OCT, fundus photography (V11, V13) (OU)
- IOP Measurement: GAT (OU) and ARGOS-SC. If available: Pascal DCT (OU)
- Patient ARGOS-SC self-measurements
- Remind subjects to promptly report any SAE that may occur at any time during the study.
- Complete the CRF and arrange the next visit.

Visit 13 is the study discharge/end of study visit. After this visit, subjects will return to standard care. The choice of keeping the implant or letting the implant be retrieved will be offered to the participating patients.

 IOP Implantdata Ophthalmic Products GmbH	Clinical Investigation Plan ARGOS-SC01_Follow-up	Revision C  Page 69 of 97
--	---	---------------------------------

## 9. STATISTICS

### 9.1 Statistical design, method and analytical procedures

The primary purpose of this investigation is to assess the long-term performance of the investigational device. In order to investigate the long-term performance of the investigational device, the data obtained from the study will be evaluated with explorative and descriptive analysis of the outcome variables described below. Generally, summary tables will be presented. These are either frequency tables (ordinal or nominal data) or summary statistics with mean, standard deviation, median, minimum, maximum, lower and upper quartile (metric data).

Outcome variables that are recorded separately for the study eye, i.e. the eye with implanted ARGOS-SC sensor, and the fellow eye, i.e. the eye without ARGOS-SC sensor, will be also analyzed separately to allow comparisons between the study and fellow eyes.

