#### 8.1.2 Description of the measures to be taken to minimize or avoid bias

All eligible patients will be enrolled.

There will be no control group for safety events. Incidence, nature and severity will be compared to literature of standalone NPGS. To allow assessment of performance, measurements of IOP with the ARGOS-SC sensor will be compared to those obtained with the standard GAT method and Pascal DCT at the same time point. To prevent possible influence of prior knowledge of the IOP value obtained with the ARGOS-SC, which is objectively displayed, measurements will always be made first with GAT/DCT. Data on all device deficiencies will be recorded.

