3.2 Study groups

ARGOS-SC System

Since this is a single arm study, there is no comparator in this study.

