8.7 Further analyses

- Vision related Quality of Life (VQoL) questionnaire at visit V09, V11 and V13.
- Visual acuity (ETDRS) on both eyes at visit V09 – V13
- Perimetry on both eyes at visit V09 – V13
- The ANTERION® from Heidelberg Engineering performed at V09 – V13
- Anterior eye segment measurement on both eyes at visit V09 – V13:
 - Optical coherence tomography (OCT), Central cornea thickness (CCT)
 - Slit-lamp biomicroscopy (Lids, Conjunctiva, Cornea, Anterior chamber, Iris Pupil, Lens, Anterior vitreous body)
 - Gonioscopy (angle open to (Shaffer), pigmentation of Trabecular meshwork)
- Posterior eye segment measurement:
 - Biomicroscopy (dilated, fundus) on both eyes at visit V09 – V13
 - Optical coherence tomography (OCT) on both eyes at visit V09 – V13

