11.3 Statistical Analysis Package – Table of Contents

11.3.1 Tables

Table 1.1	Patient Disposition
Table 1.2	Baseline Characteristics
Table 2.1.1	IOP measures: GAT and ARGOS-SC
Table 2.1.2	IOP measures: DCT and ARGOS-SC
Table 2.2.1	User Acceptance Questionnaire for Investigator
Table 2.2.2	User Acceptance Questionnaire for Patient
Table 2.2.3	Standard deviation of IOP measures: GAT and ARGOS-SC
Table 2.3.1	Vision related Quality of Life Questionnaire
Table 2.3.2	Visual acuity (study eye)
Table 2.3.3	Visual acuity (fellow eye)
Table 2.3.4	Perimetry (study eye)
Table 2.3.5	Perimetry (fellow eye)
Table 2.3.6	Heidelberg Engineering ANTERION® (study eye)
Table 2.3.7	Heidelberg Engineering ANTERION® (fellow eye)
Table 2.3.8	Anterior segment (study eye)
Table 2.3.9	Anterior segment (fellow eye)
Table 2.3.10	Posterior segment (study eye)
Table 2.3.11	Posterior segment (fellow eye)
Table 3.1.1	Adverse Events
Table 3.1.2	Serious Adverse Events
Table 3.1.3	Device-related Adverse Events
Table 3.1.4	Device-related Serious Adverse Events
Table 3.2.1	Characteristics of Adverse Events
Table 3.2.2	Characteristics of Serious Adverse Events
Table 3.2.3	Characteristics of Device-related Adverse Events
Table 3.2.4	Characteristics of Device-related Serious Adverse Events
Table 3.3.1	Device Deficiencies
Table 4.1.1	Concomitant Medication of glaucoma
Table 4.1.2	Concomitant Medication of other indication

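### The protocol intends a comparison of study and fellow eyes, but the SAP tabulates each eye separately and plans no within-patient difference or confidence interval

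*Protocol*

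**What the plan says.** Protocol 9.1 states that variables recorded separately for the study eye and the fellow eye "will be also analyzed separately to allow comparisons between the study and fellow eyes". It describes the output as frequency tables or summary statistics. Protocol 8.3.12.12 requires posterior OCT on both eyes "in order to compare study and fellow eye", and 8.3.12.8 gives the same reason for perimetry.

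SAP 8.7 lists the measures, for example "Optical coherence tomography (OCT) on both eyes at visit V09 – V13", without a method for comparing the eyes. SAP 11.3.1 has five pairs of tables, one per eye, numbered 2.3.2 to 2.3.11. They cover acuity, perimetry, ANTERION, anterior segment and posterior segment. No table or figure is listed for a difference between eyes. In SAP 11.3.3 the only listing of ophthalmic examinations is restricted to abnormal findings. SAP section 9 does not record the between-eye comparison as dropped.

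On other references, Protocol 8.1.2 says "There will be no control group for safety events" and turns to literature on standalone surgery. SAP 3.2 says "Since this is a single arm study, there is no comparator in this study".

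**The concern.** The two eyes of a patient form a matched pair. Two separate sets of means and SDs leave out the between-eye correlation, and that correlation determines how uncertain the difference is. A reader who wants the comparison named in the protocol can subtract two means, but can attach an interval only by treating the eyes as independent samples. If the eyes are positively correlated beyond a trivial level, that interval is too wide.

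There is a second, smaller problem. Protocol 9.8 uses observed cases, so if one eye is not measured at a visit the two means come from partly different patients.

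The study has one arm, so the fellow eye is the only concurrent reference for nerve fibre layer, rim width, corneal thickness, visual field and acuity. If the comparison is to inform long-term safety, its uncertainty should be stated correctly.

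**Working it through.** **Inputs from the documents.** The maximum number of patients is 24, with no minimum fixed (Protocol 9.2). Confidence intervals are two-sided 95% (SAP 8.1.3). The documents give no figure for the precision of a between-eye comparison, so there is none to reproduce. The 0.10 significance level and 80% power in Protocol 9.3 are attached to no effect size, SD or test, and Protocol 9.2 says that the sample size is not power-driven.

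**Assumptions.** The documents give neither the SD of any measure nor the between-eye correlation ρ. I take the same SD in both eyes and use it as the unit. I take ρ from 0.3 to 0.7, and also show ρ = 0.

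**Formulas.** With equal SDs, the variance of a within-patient difference is 2(1 − ρ) SD².

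- Half-width from two tables treated as independent: t(0.975, 2n − 2) × √(2/n)
- Half-width from the paired difference: t(0.975, n − 1) × √(2(1 − ρ)/n)

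**Results at n = 24.** Independent: 2.013 × √(2/24) = 2.013 × 0.2887 = 0.581 SD. Paired, with t(0.975, 23) = 2.069:

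| ρ (assumed) | √(2(1 − ρ)/24) | Paired half-width (SD) | Against 0.581 |
|---|---|---|---|
| 0 | 0.2887 | 0.597 | 3% wider |
| 0.3 | 0.2415 | 0.500 | 14% narrower |
| 0.5 | 0.2041 | 0.422 | 27% narrower |
| 0.7 | 0.1581 | 0.327 | 44% narrower |

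**Break-even.** The half-widths are equal when √(1 − ρ) = 2.013/2.069, so ρ = 1 − (2.013/2.069)², about 0.05.

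**Fewer pairs.** At ρ = 0.5 the independent and paired half-widths are 0.640 and 0.468 SD for 20 pairs, 0.722 and 0.533 for 16, and 0.847 and 0.635 for 12. The paired interval remains 25% to 27% narrower.

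**What these figures do not cover.** They apply to the difference at a single visit. The precision of its change from V09 depends on the SD of within-eye changes and on their correlation between eyes. The documents give neither, and no figure is offered here.

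**Can the pairs be recovered from the planned output?** No. Rebuilding them needs both eyes' values for each patient, and the ophthalmic listing shows abnormal findings only. The values remain in the database, so the loss is in the output and not in the data.

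**The case against.** The strongest reply is that the plan contains no faulty analysis. SAP 8.1.1 and 8.1.3 make everything descriptive and rule out tests, and no unpaired interval is planned. The half-width of 0.58 SD belongs to a calculation that a reader would have to make. This stands: the gap is a missing estimate, not a wrong one. A reader might infer reduced power or a distorted error rate, but the documents do not support that, because there is no test to which such rates could belong.

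Secondly, the gain from pairing depends on a correlation that is not documented, and equal SDs are doubtful when only one eye carries the implant. This also stands, and the size can be stated only conditionally.

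Thirdly, the fellow eye is not an exchangeable control. The study eye had glaucoma surgery and received the sensor. Protocol 8.3.12.2 leaves concomitant medication unrestricted, and SAP 8.8.3 tabulates glaucoma medication separately for the study eye. Pairing reduces noise but does not remove this bias, and a narrow interval around a confounded difference could persuade more than it should. That is a reason to report the change from V09 as well, and to label the comparison carefully.

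Fourthly, the scope is limited. These are further analyses, outside the primary and secondary endpoints. SAP 7.4 says most of the other variables are categorical, and rim width is measured only where available. The SAP shows no mock-up of these tables, so their content is inferred from the titles and SAP 8.7. Both eyes are scheduled at the same visits, and nothing documents how often one eye would be missing.

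None of this explains why a comparison named three times in the protocol has no planned estimate. The SAP already does the equivalent for the two measurement methods: the mock-up of Table 2.1.1 reports the paired ARGOS-SC minus GAT difference with SD and 95% CI.

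**Conclusion.** The point holds as a missing paired summary. The between-eye comparison is a stated purpose of the protocol, the SAP leaves it to separate tables, and the planned output does not allow its uncertainty to be worked out correctly. At 24 complete pairs, and assuming equal SDs, the paired 95% interval for the difference at one visit would be 14%, 27% or 44% narrower than one built from the separate tables at ρ = 0.3, 0.5 or 0.7. It would be about 3% wider at ρ = 0.

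A reader might go further and conclude that the comparison is much less precise than the data allow. That is not established: it depends on a correlation that the documents do not give, and on an unpaired interval that the plan does not call for. Nor do these figures show that an effect specific to the implanted eye would be missed during follow-up, because they do not address change from V09. The primary and secondary endpoints are unaffected. This is an inexpensive improvement to descriptive further analyses.

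**What to change.** In Protocol 9.1 and SAP 8.7, keep the per-eye tables and add a paired summary for each continuous measure taken on both eyes: ETDRS letters, perimetric indices, central corneal thickness, nerve fibre layer thickness, and minimum rim width where available. For each patient with both eyes measured, compute study eye minus fellow eye at each visit, and the change in that difference from V09. Report the number of complete pairs, mean, SD and 95% CI, and add the rows to the list in SAP 11.3.1.

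State that the summary is descriptive, and that the fellow eye is a reference without the sensor and not an exchangeable control. Attach no power or error-rate claims.

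The cost is SAP and protocol wording and one extra block per relevant pair of tables, with no new data, visits or patients. Patients with only one eye measured at a visit drop out of the paired row but stay in the per-eye tables. If the eyes turn out to be uncorrelated, the interval is slightly wider than one that ignores the pairing.
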